12.2. Dietary Requirements

There are no dietary requirements or restrictions for the administration of the study drug. It is recommended that study drug be administered preferably with or immediately after a meal or snack and with approximately 8 oz./240 mL of water.

12.3. Study Drugs

Study drug will consist of oral ibrexafungerp (150 mg tablets).

12.4. Ibrexafungerp Description

Study Drug Identifier: ibrexafungerp

12.4.1. Formulation, Packaging and Labelling

Ibrexafungerp citrate drug product for oral administration will be supplied as a tablet containing 150 mg of ibrexafungerp active ingredient on a free-base basis. In addition to the active ingredient, the tablet formulation also contains silicified microcrystalline cellulose, crospovidone, mannitol, colloidal silicon dioxide, magnesium stearate (non-bovine) and butylated hydroxyanisole.

Oral tablets will be supplied in blister packs of four 150 mg tablets per blister. Each blister constitutes one day's dosing of 300 mg BID. Labels on the blisters will contain study medication information and any other information required by applicable regulations and may include the following information:

- Product Name
- Sponsor Name
- Study Protocol Number
- Place to write the subject number
- Number of tablets per blister pack
- Dosing instructions
- Storage conditions (e.g. room temperature 15°C – 25°C
- Caution Statement: e.g. "Caution: New Drug – Limited by Federal (United States) Law to Investigational Use Only"

12.4.2. Storage and Stability

The pharmacist or appropriate designee at each clinical research site will be responsible for the study drug. For long-term storage at the site, study drug supplies provided in blisters must be kept in a secure area (e.g., locked cabinet) and stored at room temperature.

12.5. Drug Accountability

The investigator or designee will inventory and acknowledge receipt of all shipments of the study drug. Drug accountability logs will be used to maintain accurate records of receipt, dispensing, administration to each subject and return of drug. A study monitor will periodically check the supplies of investigational products held by the site to verify accountability of all study drugs. At the conclusion of the study after final drug accountability has been completed by the monitor, all unused study drug and all empty/partially used blisters will be returned to the Sponsor or destroyed on site if the site has procedures in place for study drug destruction.

Drug supplies will be maintained in a secure, limited-access storage area under the recommended storage conditions (see Section 12.4.2).

The study drug supplied for this study is only for use in subjects properly consented and enrolled under this protocol. A study site designee (e.g. pharmacist, study nurse/coordinator) will:

- Record the treatment in the appropriate drug accountability log
- Report and document any study medication issues such as crushed or broken tablets
 - All product quality complaints should be reported to the Sponsor
- Collect blister packs (containers) and count the number of tablets remaining at the TOC visit.
- Record any unused or remaining drug in the drug accountability log and eCRF and note any discrepancies and reason for discrepancies

12.6. Subject Compliance with Study Drug Dosing

Subjects will be instructed to bring the assigned blister packs of study medication (including empty blister packs) with them to the TOC visit to assess treatment compliance. Compliance will be assessed based on remaining tablets as compared to what should have been taken. Details of treatment including any missing dose will be recorded on the eCRF. Sites are encouraged to contact the medical monitor or sponsor for concerns of compliance with the treatment regimen, especially for subjects who miss doses due to problems with tolerability.

13. NON-STUDY TREATMENTS

13.1. Prior and Concomitant Medications

All medications (including prescription and over-the-counter medications, supplements, and herbal products) taken from 30 days before the Screening Visit (Day -2 [\pm 1]) through the TOC

visit will be recorded in the eCRF. Only the use of antifungal medications, medications used to treat vaginal infections, vaginal (topical) medications, antibiotics for any reason or any other medications to treat a study-drug related AE will be recorded after the TOC visit through the last study visit (FU). Start and stop dates of concomitant medications will be recorded in the eCRF. Prior and concomitant medications will be reviewed and recorded at all scheduled and unscheduled study visits.

13.2. Prohibited Medications

Medications specifically not permitted in the exclusion criteria (Section 11.2) include the following:

- Non-study systemic or topical antifungal therapy
- Topical vaginal corticoids
- Topical (vaginal) contraceptives
- Other investigational drug(s)
- Select strong CYP3A4/5 inhibitors, CYP3A4/5 inducers and select P-gp substrates.

See Section 21 ([Appendix 1](#)) for the full list of prohibited medications.

13.2.1. Medications to be Administered with Caution and Monitored as Appropriate

The following medications must be administered with caution and must be monitored as appropriate:

- CYP3A4 substrates, including but not limited to sirolimus, tacrolimus warfarin, cyclosporine and amiodarone
- Organic anion-transporting polypeptide 1B3 (OATP1B3) substrates

See Section 21 ([Appendix 1](#)) for the full list of medications to be administered with caution.

13.3. Study Restrictions

There are no study restrictions other than those described in Section 11.2 (Exclusion Criteria), Section 12.2 (Dietary Requirements) and Section 13.2 (Prohibited Medications).

14. STUDY PROCEDURES

The following sections provide a description of the individual study procedures to be performed during the conduct of the study. Detailed schedules of study assessments are provided in the Schedule of Visits and Procedures in [Table 1](#).

14.1. Informed Consent

Every study subject must provide written informed consent at Screening, prior to participating in any Screening evaluations or any other study activities (see Section [19.3](#)).

14.2. Assignment of Subject Number

At Screening, all subjects who have signed an ICF will receive a unique subject identification (ID) number, which will consist of a site number followed by a 2-digit sequentially assigned subject number starting at 01, at each site. The subject numbers assigned to eligible subjects will be recorded in the eCRF. This number will be unique to each subject and will be used to identify the subject throughout the study.

Subjects who are screen failures or who are not eligible for enrollment will be recorded as such in the eCRF. For subjects who sign an ICF (i.e., are assigned a subject number) but are NOT enrolled because they do not meet all of the inclusion/exclusion criteria, the applicable screening visit pages of the eCRF will be completed. The criteria that were not met for enrollment will be documented in the eCRF.

14.3. Inclusion and Exclusion Criteria

All inclusion and exclusion criteria will be reviewed at Screening (-2 \pm 1) and at Baseline (Day 1) to ensure that the subject qualifies for the trial. Screening and Baseline can be on the same day, if applicable.

14.4. Medical History and Demographics

During the Screening visit, a complete medical history for the prior year will be recorded for each subject. The medical history will include previous and current medical diagnoses and major surgical procedures. Subject demographics such as age, sex, race, and ethnicity will also be collected.

14.5. Abbreviated Physical Examination

An abbreviated physical examination, including general appearance and an overall examination of body systems, will be conducted at Screening, TOC visit, and at any unscheduled visit, if needed.

14.6. Urine Pregnancy Test

A urine pregnancy test based on the measurement of human chorionic gonadotropin with a sensitivity of at least 25 international units per liter will be performed at Screening and at unscheduled visits, if needed, by the local laboratory for all subjects of childbearing potential. The pregnancy test results will be reviewed at Baseline (Day 1) before administration of study drug.

14.7. Safety Laboratory Tests

Safety laboratory tests will be performed by a qualified local laboratory. Samples for safety laboratory tests will be collected at the Screening, TOC, and at any unscheduled visit, if needed. If indicated, these may be done more frequently as follow up to a laboratory abnormality.

The following laboratory parameters will be determined:

14.7.1. Hematology

- White blood cell (WBC) count
- Hemoglobin (HgB)

- Red blood cell (RBC) count
- Platelet count
- Differential WBC count will include percentages for lymphocytes, monocytes, eosinophils and basophils,
- and absolute counts for neutrophils, lymphocytes, atypical lymphocytes, monocytes, eosinophils and basophils.

14.7.2. Blood Chemistry

- Glucose
- Albumin
- Sodium
- Potassium
- Alkaline Phosphatase
- Creatinine
- Total creatine phosphokinase (CPK)
- Aspartate aminotransferase (AST/SGOT)
- Alanine aminotransferase (ALT/SGPT)
- Gamma glutamyl transferase (GGT)
- Bilirubin (total, direct and indirect)
- Total protein

14.8. Rating of Vulvovaginal Symptoms by the Subject Using the VSS Scale

Subjects will be asked to rate their vulvovaginal symptoms at Screening, Baseline (Day 1), during telephone interviews on Days 3, 5 and 7, at the TOC visit and at the FU visits.

Subjects will also assess their symptoms at unscheduled visits, as needed.

If the subject experiences persistence or worsening or recurrence of symptoms that per the investigator's assessment (e.g. symptoms ≥ 4) warrant the use of rescue antifungal therapy, the rating of the symptoms that led to the use of rescue antifungal therapy must be documented in the eCRF and a vaginal examination with rating of signs by the investigator should be completed. If the investigator's rating of the vulvovaginal signs and vaginal samples collection are not possible prior to the initiation of the rescue therapy, they should still be completed as soon as possible after rescue therapy is initiated.

Subjects will rate their symptoms of infection using the VSS Scale, where each vulvovaginal symptom will be given a numerical rating based on severity, as follows:

- Itching: absent = 0; mild = 1; moderate = 2; severe = 3
- Burning: absent = 0; mild = 1; moderate = 2; severe = 3
- Irritation: absent = 0; mild = 1; moderate = 2; severe = 3

14.9. Vulvovaginal Samples for Identification of Other Pathogens and Vaginal pH

A vulvovaginal specimen will be obtained at the Screening visit for local vaginal pH determination. This sample will also be tested by a local qualified laboratory to rule out bacterial vaginosis and *Trichomonas vaginalis*. Testing for *Neisseria gonorrhoeae*, *Chlamydia trachomatis* or *Herpes* virus will also be conducted by a qualified local laboratory if clinically indicated. Vaginal samples will be tested for bacterial vaginosis, *T. vaginalis*, *N. gonorrhoeae*, *C.*

trachomatis or *Herpes* virus at unscheduled visits, if needed. Samples should be collected prior to the initiation of rescue therapy, and if not possible, it should still be completed as soon as possible after rescue therapy is initiated. If there is persistence or recurrence of vulvovaginal symptoms, additional vulvovaginal specimens will be collected at the TOC and at the FU visits.

Procedures for collecting and shipping vulvovaginal samples to the central laboratory will be described in the laboratory manual.

14.10. Vulvovaginal Samples for KOH and Fungal Culture

At Screening, a vulvovaginal specimen will be obtained for direct microscopic examination with 10% KOH. Subjects must have a positive KOH test at screening to be enrolled. The screening KOH will be assessed at the site by the investigator or qualified designee. A vaginal sample will also be obtained at screening, at the TOC and at the first FU visit at 14 days after EOT for fungal culture and species identification by the central laboratory and for susceptibility testing against ibrexafungerp and additional antifungal agents (per CLSI M27-A3 guidelines). If there is persistence or recurrence of vulvovaginal symptoms, additional vulvovaginal specimens will be collected for KOH testing at the TOC and at the FU visits, and for fungal culture at the FU visits. Samples will also be obtained at any unscheduled visit, if needed.

If the subject experiences persistence or worsening or recurrence of symptoms that per the investigator's assessment (e.g. symptoms ≥ 4) warrant the use of rescue antifungal therapy, the subject may be enrolled into Treatment Cycle 2 and receive additional treatment with ibrexafungerp for a period up to 14 days as recommended by the investigator and following discussion with the sponsor.

Whether or not a subject enters Treatment Cycle 2, or be prescribed rescue therapy, a vaginal examination with collection of samples for KOH (assess at the site) and culture should be completed prior to initiation of Treatment Cycle 2 or rescue therapy. If the KOH test is negative, the investigator should consider other causes for the persistence or worsening of the symptoms and antifungal rescue medication may not be indicated. If the collection of the vaginal culture is not possible prior to the initiation of the rescue therapy, it should still be collected as soon as possible after rescue therapy is given.

14.11. Rating of Vulvovaginal Signs by the Investigator Using the VSS Scale

The investigator (or qualified designee) will perform vulvovaginal examinations to rate the subject's signs of infection at the Screening, TOC and first FU visits at 14 days after EOT. The vulvovaginal examination will be repeated at the rest of the FU visits only if the subject presents with symptoms. Otherwise, no additional vulvovaginal examination will be conducted, or signs rated. Vulvovaginal examinations may be conducted at unscheduled visits, if needed.

If the subject experiences persistence or worsening or recurrence of symptoms that per the investigator's assessment (e.g. symptoms ≥ 4) warrant the use of rescue antifungal therapy, the subject may be enrolled into Treatment Cycle 2 and receive additional treatment with ibrexafungerp for a period up to 14 days as recommended by the investigator and following discussion with the sponsor.

Whether or not a subject enters Treatment Cycle 2, or be prescribed rescue therapy, a vaginal examination with rating of signs by the investigator should be completed prior to initiation of rescue therapy. If the investigator's rating of the vulvovaginal signs is not possible prior to the initiation of the rescue therapy, it should still be completed as soon as possible after rescue therapy is initiated.

Investigators will assess the signs of infection using the VSS Scale provided in Section 21 [Appendix 2]), a standardized, predefined scale where each sign of the vagina and/or vulva will be given a numerical rating based on severity, as follows:

- Edema: absent = 0; mild = 1; moderate = 2; severe = 3
- Erythema: absent = 0; mild = 1; moderate = 2; severe = 3
- Excoriation or fissures: absent = 0; mild = 1; moderate = 2; severe = 3

Other findings will be recorded using the most relevant medical term in the abbreviated physical examination page of the eCRF.

14.12. Quality of Life (QOL) Questionnaire

Subjects will complete a QOL questionnaire at Baseline, TOC and at the follow-up visits.

14.13. Randomization

This is an open label study. Subjects will be randomized to treatment and stratified by group based on the *Candida* species and presence or absence of underlying conditions.

14.14. Study Drug

At Baseline (Day 1), eligible subjects will have their Day 1 dose administered in the clinical research unit and will be dispensed enough study medication for either single day BID dose, or for BID dosing for 3 or 7 consecutive days as explained in Section 12.1.

14.15. Study Drug Dosing

Treatment Cycle 1 applicable to all subjects: The first study drug dose (Day 1) will be administered at the clinical research center and the subsequent dose(s) will be self-administered by the subjects at approximately 12 ± 3 -hour intervals at home.

NOTE: If administering the first dose at the study center would complicate the administration of the second dose 12 hours later (e.g. first dose at 3 p.m. will require second dose at 3 a.m.), the subject can self-administer both Day 1 doses at home to allow for a more convenient dosing schedule (e.g., 8 p.m. and 8 a.m.). Details of study treatment groups and dietary requirements for treatment administration are provided in Section 12.1 and Section 12.2, respectively.

Treatment Cycle 2: A second treatment cycle will be allowed for subjects who did not achieve sufficient clinical improvement (e.g. VSS remains ≥ 3) on the randomized treatment (Cycle 1) as evaluated at the TOC and FU1 visits. A second treatment cycle will also be allowed for subjects with clinical cure/improvement/success who experience a recurrence before the last FU visit.

During Cycle 2, subjects may receive additional treatment with ibrexafungerp for a period up to 14 days as recommended by the investigator and following discussion with the sponsor.

14.16. Study Drug Collection and Treatment Compliance Evaluation

Treatment compliance will be reviewed by the investigator or designee at the TOC visit. Subjects will be instructed to bring all blister packs (including empty blister packs) of study medication with them to the visit to assess treatment compliance. Further details are available in Section [12.5](#).

14.17. Vital Signs

Vital signs, including blood pressure (systolic and diastolic), heart rate and body temperature will be measured at screening and at the TOC visit as well as at unscheduled study visits, if needed.

14.18. Prior and Concomitant Medication Review

All medications (including prescription and over-the-counter medications, supplements, and herbal products) taken from 30 days before Screening visit through the TOC visit will be recorded in the eCRF. Only the use of other antifungal medications, medications used to treat vaginal infections, vaginal (topical) medications and antibiotics for any reason or any other medications to treat a study-drug related AE will be recorded after the TOC visit through the last study visit. Start and stop dates of concomitant medications will be recorded in the eCRF. Prior and concomitant medications will be reviewed and recorded at all scheduled and unscheduled study visits.

See Section [13.2](#) for prohibited medications, medications to be administered with caution and further details for non-study treatments.

14.19. Adverse Event Monitoring

AEs will be recorded and reviewed at all scheduled and unscheduled study visits from the time the ICF is signed through TOC visit. New AEs starting after TOC will be recorded only if they led to the use of other antifungal medications or topical vaginal treatment, if they are a vaginal bacterial or parasitic infection, or if they are deemed related to the previously administered study drug. See Section [16](#) for further reference.

15. STUDY SCHEDULE

Detailed schedules of all study visits and procedures are presented in Schedule of Visits and Procedures ([Table 1](#)).

The actual visits will be dependent on the Dosing Group i.e there may be overlapping visits.

Subjects entering Treatment Cycle 2, will follow the same Schedule of Visits and Procedures, starting with Baseline visit and may have visits that are Not Applicable during Treatment Cycle 1.

Table 1: Schedule of Visits and Procedures (Study SCY-078-307b)

Visit	V1 Screening ^a	V2 Baseline ^a	At Home	V3 TOC	V4 FU	V5 FU	V6 FU	V7 FU	Unscheduled Visits ^b
Day (allowable window)	Day -2(±1)	Day 1	Days 2-7	14 ±3 days post Baseline	14 ±3 days post EOT	30±4 days post Baseline	30 ±4 days post EOT	60 ±4 days post EOT	
Study Procedures									
Informed consent	X								
Enrollment and assignment of Subject ID number	X								
Inclusion/exclusion criteria ^c	X	X							
Medical history and demographics	X								
Abbreviated physical exam	X			X					If needed
Vital Signs ^k	X	X		X					If needed
Urine pregnancy test ^c	X			X					If needed
Safety laboratory blood tests ^d	X			X					If needed

Visit	V1 Screening ^a	V2 Baseline ^a	At Home	V3 TOC	V4 FU	V5 FU	V6 FU	V7 FU	Unscheduled Visits ^b
Day (allowable window)	Day -2(±1)	Day 1	Days 2-7	14 ±3 days post Baseline	14 ±3 days post EOT	30±4 days post Baseline	30 ±4 days post EOT	60 ±4 days post EOT	
Rating of vulvovaginal symptoms by the Subject^e	X	X	X	X	X	X	X	X	If needed
Vaginal Examination and rating of vulvovaginal signs by the Investigator^e	X			X	X	If symptoms	If symptoms	If symptoms	If needed
Vulvovaginal sample for other pathogens^e	X			If needed	If needed	if needed	If needed	If needed	If needed
Vulvovaginal sample for KOH and pH^e	X			If symptoms	If symptoms	If symptoms	If symptoms	If symptoms	If needed
Vulvovaginal sample for fungal culture^e	X			X	X	If symptoms	If symptoms	If Symptoms	If needed
Quality of Life Questionnaire		X		X	X	X	X	X	
Study drug dosing		X	X						
Study drug container(s) collection and subject data reviewed				X					
Phone Contact^h			X						
Prior and concomitant medication reviewⁱ	X	X	X	X	X	X	X	X	X
AE monitoring^j	X-----X				X	X	X	X	X

Abbreviations: AE = adverse event; D = day; TOC = test of cure; V = visit; FU = follow up

- a) Screening and Baseline may occur on the same day.
- b) Unscheduled visits can occur if the investigator determines there is a need for one outside of the scheduled per protocol visits.
- c) Results should be reviewed prior to enrollment at Baseline (Day 1).
- d) Hematology and blood chemistry. Safety laboratory tests will be performed by a qualified laboratory.
- e) A vaginal examination with rating of signs by the investigator will be completed at the TOC visit. If the subject experiences persistence or worsening or recurrence of symptoms, after the baseline visit (e.g. symptoms ≥ 4), that warrant the use of rescue antifungal therapy, the symptoms that led to the use of rescue antifungal therapy must be documented in the eCRF. Additionally, vulvovaginal samples should be obtained for KOH testing and pH measurement (both at the clinical research unit), fungal culture (central laboratory) and investigation of other pathogens such as bacterial vaginosis and *Trichomonas vaginalis* (at the local lab). If the investigator's rating of the vulvovaginal signs and vaginal samples collection are not possible prior to the initiation of the rescue therapy, they should still be completed as soon as possible after rescue therapy is initiated.
- f) Vulvovaginal examinations will be repeated at the FU visits only if the subject presents symptoms. Otherwise, no additional vulvovaginal examination will be conducted or signs rated.
- g) The first study drug dose (Day 1) will be administered at the clinical research center and the subsequent dose(s) will be self-administered by the subjects at approximately 12 ± 3 hour intervals at home.
- h) The Day 3, 5, and 7 phone contacts will be used to evaluate symptom resolution, AEs, and concomitant medications.
- i) Only the use of antifungal medications, vaginal (topical) medications, antibiotics for any reason or any other medications to treat an AE will be recorded after the TOC visit through the last study visit (FU).
- j) New AEs starting after TOC will be recorded only if they led to the use of other antifungal medications or topical vaginal treatment, if they are a vaginal bacterial or parasitic infection, or if they are deemed related to the previously administered study drug
- k) Blood pressure (systolic and diastolic), heart rate and body temperature

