10.1.1. Study Visits

The study will consist of a Screening visit on Day -2 (± 1), Baseline visit on Day 1 (if applicable, the Screening and Baseline visits can both be done on Day 1), Phone contacts on Days 3, 5 and 7 (± 1), a TOC visit 14 (± 3) days after Baseline, FU visits at: 14 (± 3) days after EOT, 30 (± 4) after Baseline, 30 (± 4) after EOT and 60 (± 4) days after EOT.

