10.1.1.4. TOC visit (14 \pm 3 days after Baseline)

At this visit, study drug container(s) will be returned, reviewed, and treatment compliance evaluated. The investigators and the subjects will again rate the signs and symptoms of infection on the VSS Scale and the subjects will complete a QOL questionnaire.

Vulvovaginal samples for fungal culture, species identification, and antifungal susceptibility testing will be obtained and sent to a designated central laboratory. Additional vaginal samples will be obtained for a KOH test and pH measurements by the local laboratory if symptoms persist or have worsened. AEs and/or concomitant medications will be evaluated.

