11.2. Exclusion Criteria

A subject will be excluded from participation in the study if she meets any of the following exclusion criteria:

1) Subject has any vaginal condition other than VVC that may interfere with the diagnosis or evaluation of response to therapy, such as concurrent causes of vulvovaginitis and/or cervicitis including bacterial vaginosis, *Trichomonas*, *Herpes* virus, *Neisseria gonorrhoeae*, *Chlamydia*, symptomatic human papillomavirus infection, or other mixed infections.

- 2) Subject received systemic and/or topical vaginal antifungal treatment, including prescription or over-the-counter products, within 7 days prior to the Screening visit. **Note: The screening visit may be rescheduled if required.**
- 3) Subject is receiving or anticipates requiring treatment with the prohibited medications within the specified timeframes per Appendix I.
- 4) Subject has active menstruation at the Screening visit. Note: **The Screening visit may be rescheduled if required.**
- 5) Subject has a history of or an active cervical/vaginal cancer.
- 6) Subject has a known hypersensitivity to any of the components of the formulation.
- 7) Subject has participated in any other investigational study within at least 30 days (or 5.5 half-lives of the investigational product) before signing the ICF.
- 8) Subject has received prior treatment with ibrexafungerp.
- 9) Subject has any other condition or laboratory abnormality (such as severe hepatic impairment) that, in the judgment of the investigator, would put the subject at unacceptable risk for participation in the study or may interfere with the assessments included in the study.
- 10) Subject is unlikely to comply with protocol requirements.

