12. STUDY TREATMENTS

12.1. Study Treatment Groups

Treatment Cycle 1 – ALL randomized subjects:

Subjects who meet all the inclusion and none of the exclusion criteria will be randomized to treatment and stratified by group based on the *Candida* species and presence or absence of underlying conditions. Subjects will receive open-label oral ibrexafungerp 300 mg BID for one, three or seven consecutive days per the table below:

Ibrexafungerp Treatment Groups:

Treatment Group	Criteria	*Ibrexafungerp Dose (300mg AM and 300mg PM) Randomization and Stratification
Group A	Subjects without underlying medical conditions AND known to have isolates other than C glabrata , C krusei , C auris	1 Day dosing N=50
Group B	Subjects with underlying medical conditions: DM, immunocompromised conditions (e.g. HIV), debilitation, immunosuppressive therapy (e.g. corticosteroids), recurrent VVC (≥ 3 episodes/year) AND/OR known to have C glabrata , C krusei or C auris isolates	3 Days OR 7 Days dosing Randomized 1:1 N=50:50

*Days of treatment is per CDC Guidelines (<https://www.cdc.gov/std/treatment-guidelines/candidiasis.htm>)

Enrollment will continue until the target number in each cohort is reached.

Treatment Cycle 2: A second treatment cycle will be allowed for subjects who did not achieve sufficient clinical improvement (e.g. VSS remains ≥ 3) on the randomized treatment (Cycle 1) as evaluated at the TOC and FU visits. A second treatment cycle will also be allowed for subjects with clinical cure/improvement/success who experience a recurrence before the last FU visit. During Cycle 2, subjects may receive additional treatment with ibrexafungerp for a period up to 14 days as recommended by the investigator and following discussion with the sponsor.

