6.4.3.3. Additional Estimates

For the subgroup analyses by Candida species, only descriptive statistics will be provided; no statistical testing will be performed due to possible small sample size.

All other efficacy data will be summarized, but not subject to formal statistical analysis.

6.5 Treatment Cycle 2

A second treatment cycle will be allowed for subjects who did not achieve sufficient clinical improvement (e.g. VSS remains ≥ 3) on the randomized treatment (Cycle 1) as evaluated at the TOC and FU visits. A second treatment cycle will also be allowed for subjects with clinical cure/improvement/success who experience a recurrence before the last FU visit. During Cycle 2, subjects may receive additional treatment with ibrexafungerp for a period up to 14 days as recommended by the investigator and following discussion with the sponsor.

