6.5.1. Efficacy Analysis (Treatment Cycle 2)

The proportion of Cycle 2 subjects enrolled in MITT, ITT and PP populations will be summarized in each table.

Secondary, and exploratory efficacy analysis will be analyzed the same as for cycle 1.

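### In Cycle 2 the test-of-cure visit stays at Baseline+14 days although dosing may last 14 days, so one Cycle 2 TOC rate pools on-drug and off-drug assessments

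*Protocol*

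**What the plan says.** Protocol section 15 gives Cycle 2 no timetable of its own: "Subjects entering Treatment Cycle 2, will follow the same Schedule of Visits and Procedures, starting with Baseline visit". In that schedule TOC is tied to Baseline, not to end of treatment (EOT). Protocol section 10.1.1 has "a TOC visit 14 (± 3) days after Baseline", and Table 1 agrees. At TOC every subject is cultured and scored (Protocol section 10.1.1.4): "Vulvovaginal samples for fungal culture, species identification, and antifungal susceptibility testing will be obtained and sent to a designated central laboratory" and "The investigators and the subjects will again rate the signs and symptoms of infection on the VSS Scale".

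Cycle 2 course length is not fixed. Protocol section 12.1 allows "additional treatment with ibrexafungerp for a period up to 14 days as recommended by the investigator", after discussion with the sponsor, and SAP section 6.5 repeats the 14-day maximum.

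For the analysis, SAP section 6.5.1 says: "Secondary, and exploratory efficacy analysis will be analyzed the same as for cycle 1". Under SAP sections 4.2.2 and 6.4.2.2, that brings in clinical improvement, clinical success, mycological response, cure combined with mycological response, and change in VSS score, each at TOC and at the follow-up visits. SAP section 6.4.2.1 defines mycological eradication as a negative culture.

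A visit tied to EOT also exists. V4, at EOT+14 ±3 days, has a scheduled culture and sign rating (Protocol sections 10.1.1.5, 14.10 and 14.11).

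**The concern.** A test-of-cure culture is meant to show whether the organism is gone once treatment has stopped. A culture taken during dosing, or a day or two after it, cannot separate eradication from suppression by the drug. In Cycle 1 the longest course is 7 days, so a TOC tied to Baseline always falls after the last dose. In Cycle 2 the course may be twice as long and the anchor does not move. No section re-anchors the Cycle 2 TOC to EOT.

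Because course length varies between subjects, the percentage labelled Cycle 2 TOC would mix assessments made well after treatment with some made during it. The SAP provides no breakdown by course length. At stake is the meaning of the Cycle 2 TOC results, mycological response above all, and whether they can be read beside Cycle 1 TOC.

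**Working it through.** The plan gives no figure to reproduce here; the check is calendar arithmetic.

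**Inputs**
- Baseline is Day 1 of the cycle (Protocol section 10.1.1).
- TOC is Baseline + 14 ±3 days (Protocol section 10.1.1), so Day 15, window Days 12 to 18.
- The last dosing day is Day *d*. In Cycle 1, *d* = 1, 3 or 7; in Cycle 2, *d* is at most 14 (Protocol section 12.1, SAP section 6.5).
- V4 is EOT + 14 ±3 days, so Day *d* + 14, window *d* + 11 to *d* + 17.
- Assumption: dosing starts on Day 1 of the cycle and runs without gaps.

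**Formula**

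Days from last dosing day to TOC = 15 − *d* at the nominal visit, 12 − *d* at the earliest, 18 − *d* at the latest. A window day is on drug if it is no later than Day *d*.

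| Last dosing day *d* | Days off drug at nominal TOC (range) | TOC window days on drug, of 7 | V4 falls on Day (range) |
|---|---|---|---|
| 1 | 14 (11 to 17) | 0 | 15 (12 to 18) |
| 3 | 12 (9 to 15) | 0 | 17 (14 to 20) |
| 7 | 8 (5 to 11) | 0 | 21 (18 to 24) |
| 8 | 7 (4 to 10) | 0 | 22 (19 to 25) |
| 9 | 6 (3 to 9) | 0 | 23 (20 to 26) |
| 12 | 3 (0 to 6) | 1 | 26 (23 to 29) |
| 13 | 2 (−1 to 5) | 2 | 27 (24 to 30) |
| 14 | 1 (−2 to 4) | 3 | 28 (25 to 31) |

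For *d* = 14: 15 − 14 = 1, 12 − 14 = −2, 18 − 14 = 4. Days 12, 13 and 14 of the window are dosing days.

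**Sensitivity to day numbering.** If TOC is read as Day 14 ±3, every interval shortens by one day. A 14-day course then gives 0 (−3 to 3), with 4 of 7 window days on drug, and on-drug sampling becomes possible from *d* = 11.

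**A yardstick.** The documents give no half-life for ibrexafungerp, so residual drug cannot be estimated. The only drug-free interval they offer is the entry rule in Protocol section 11.2, which excludes a subject if "Subject received systemic and/or topical vaginal antifungal treatment, including prescription or over-the-counter products, within 7 days prior to the Screening visit". Set against 7 days, the nominal TOC is too early for *d* ≥ 9 (15 − 9 = 6) and the whole window is too early for *d* ≥ 12 (18 − 12 = 6).

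**The alternative visit.** At V4 the interval is (*d* + 14 ±3) − *d* = 14 ±3, that is 11 to 17 days off drug whatever the course length.

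**The case against.** The strongest reply is that this is mainly a labelling matter. V4 results are already summarised among the follow-up visits, so off-drug Cycle 2 data will exist and be reported. SAP section 6.5.1 names only secondary and exploratory analyses, so the primary endpoint on its own is not listed for Cycle 2. Fourteen days is a maximum, and the documents say neither how many subjects will enter Cycle 2 nor how long their courses will be. At 8 days or fewer the nominal TOC is at least 7 days after the last dose. All of this stands, and it limits the weight of the point. It does not answer the point, because nothing says which visit defines Cycle 2 response, and the visit called test of cure may fall during dosing.

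Three stronger readings are tempting and are not supported.

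- **That the protocol breaks its own washout.** The 7-day rule is an entry criterion on earlier antifungals at Screening. The protocol does not call it a washout and does not apply it to study drug or to TOC. It is a yardstick, and no rule is breached.
- **That longer Cycle 2 courses will look better.** Suppression of culture could push that way, but the course is as the investigator recommends, and harder cases may receive longer ones. The net direction is unknown. For the VSS-based outcomes the documents give no basis for a direction either.
- **That Cycle 1 needs the same correction.** The 7-day arm is 5 to 11 days off drug at TOC and falls below 7 only on Days 12 and 13 of the window. The 3-day arm (9 to 15 days) never does. Dropping cultures taken within 7 days of the last dose would remove subjects from the 7-day arm only, a one-sided exclusion after randomisation. A common time from Baseline is a legitimate basis for the randomised comparison, and the V4 summary already shows the two arms aligned on EOT.

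**Conclusion.** The point holds for Cycle 2. Followed as written, the plan can report an on-drug culture as mycological eradication at a visit called test of cure: after a 14-day course TOC falls 1 day after the last dosing day (range −2 to 4). Across permitted course lengths, one Cycle 2 TOC percentage pools nominal drug-free intervals from 14 days down to 1 day, and window timing takes the shortest onto drug. That percentage cannot be interpreted as eradication or set against Cycle 1 TOC.

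This rests on Baseline being Day 1, on uninterrupted dosing from that day, and on some subjects receiving courses near the maximum. The effect on the reported rates cannot be sized, because Cycle 2 numbers, course lengths and drug persistence are not given. The Cycle 1 primary endpoint and the randomised 3- versus 7-day comparison are untouched by Cycle 2 timing. The matter concerns secondary and exploratory summaries in an optional retreatment phase of an exploratory study, but it should be settled before database lock.

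**What to change.** In SAP section 6.5.1:

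1. Name V4 (EOT+14 ±3 days) as the visit that defines Cycle 2 clinical and mycological response, including the combined endpoint.
2. Label the Cycle 2 TOC as an on-treatment or early post-treatment assessment, and summarise it by course length or by days since last dose.
3. State how a missing V4 is handled. Protocol section 18.4 assigns failure only when the TOC assessment is missing, and SAP section 6.1.2 imputes nothing unless specified.

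Two inconsistencies need reconciling at the same time. Footnote f to Table 1 limits follow-up examinations to subjects with symptoms, whereas Table 1 itself and Protocol sections 10.1.1.5 and 14.11 make the V4 examination routine. Table 1 also shows home dosing on Days 2 to 7 only, which does not match the Cycle 2 dosing text. Which of the conflicting passages should stand is for the sponsor to decide.

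No exclusion of Cycle 1 cultures is needed.

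The main change is SAP wording, since V4 culture and sign rating are already scheduled; no visit, sample or dosing change is called for. The cost is one added missing-data rule and probably somewhat more missing data at V4 than at TOC, by an amount the documents do not allow us to estimate.
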